## STATISTICAL ANALYSIS

Linear mixed effects models will be applied to assess the impact of Treatment Distribution (Intensive vs Distributed), Biofeedback (Ultrasound vs No Ultrasound) and Modality (Teletherapy vs Face-to-face) on percent target sounds correct from untreated phrase probes. The dependent variable is the percentage of correct speech sounds at each time point (week 0, 5, 10 and 15). Fixed effects include Groups as the combination of Treatment Distribution, Biofeedback and Modality, time points and their interaction. Participants are included as random effects. Appropriate correlation structure between observations from a single subject is selected via visual examination of fitted residual variance-covariance matrix and comparing Akaike Information Criteria (AIC) values. Time points are modeled as categorical variable instead of continuous variable with smaller AIC values. The final model includes each participant's baseline (pre-treatment) accuracy at week 0 as a covariate, using heterogeneous first-order autoregressive variance and correlation structure. No missing values are imputed and no multiplicity adjustment are applied. Restricted maximum likelihood is used to estimate covariance parameters and Kenward and Roger's method is used for approximating degrees of freedom (Kenward & Roger, 1997). Specific contrasts are constructed to test the difference between treatment groups in terms of the improvement between baseline and week 5, 10, 15, respectively. Interaction terms at each time points between Treatment Distribution and Biofeedback are also tested. The primary analysis is a comparison of change in percent correct from pre-treatment to the 10-week period (after all participants had completed 20 hours of therapy). Additional analyses are conducted after 5 weeks, in which the Intensive group had completed 20 hours and the Distributed group had completed 10 hours of treatment, and also at

15 weeks to assess retention following the conclusion of treatment. Furthermore, we examine the effects of treatment in an analysis that holds constant number of treatment sessions rather than number of weeks (i.e., short-term generalization following 20 hours of therapy, plus retention 5 weeks later). All tests of significance were claimed at 2-tailed alpha = .05.

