****The 2 least accurate of the 3 individual phrase probes will be selected as therapy targets.**

Progress monitoring Assessment (~40 minutes): Conducted after 5 weeks, 10 weeks, and 15 weeks.

1. Multisyllabic Word Repetition Task ([name] & Edwards, 2007). ~10 minutes. Participants will repeat multisyllabic words of 2-5 syllables after the word is presented via computer. Percent consonants correct, percent lexical stress correct, and number of syllable segregations will be obtained.
2. Multisyllabic Picture Naming. ~5 minutes. Participants will name 30 researcher-selected multisyllabic words presented via pictures on PowerPoint slides. Percent consonants correct, percent lexical stress correct, and number of syllable segregations will be obtained.
3. Word Inconsistency subtest of Linguisystems Articulation Test (Bowers & Huisinigh, 2011). ~5 minutes. Participants will name 12 multisyllabic pictures 3 times each following an initial model (e.g., "Say *eyelashes* three times). Productions will be evaluated on whether the 3 trials are consistent (C) or inconsistent (I). Additionally. Percent consonants correct, percent lexical stress correct, and number of syllable segregations will be obtained from the first production of each set.
4. Phrase repetition task. ~10 minutes. Participants will repeat phrases and short sentences containing multisyllabic words after the phrase/sentence is presented via computer (e.g., "factual discussion;" "Renew my newspaper subscription."). Percent consonants correct, percent lexical stress correct, and number of syllable segregations will be obtained.
5. Three Individual Phrase Probe Lists. ~5 minutes each, 15 minutes total. Based on speech sound errors observed in Baseline 1, specific error patterns will be identified. Individual probes addressing an error pattern will be administered. Participants will read a list of 20 phrases containing the target pattern (e.g., for onset /l/ examples might be: "please go left" and "light the flame"). Percent accuracy will be collected on number of target sounds produced correctly out of 40 using a binary scoring system (i.e., incorrect = 0; correct = 1).
6. Ultrasound Safety Form (for those receiving US biofeedback). ~5 minutes. Administer a short questionnaire to participant and parent to ensure that procedures and methods continue to be safe and are without adverse effect.

Treatment Design

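### The SAP uses week-0 accuracy in the primary model both as a response and as a covariate; read literally with one row per child per visit, the REML fit has no maximum, and the text does not fix which primary estimate is meant.

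*SAP*

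**What the plan says.** All of the relevant text is in the SAP's Statistical Analysis section.

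- Response: "The dependent variable is the percentage of correct speech sounds at each time point (week 0, 5, 10 and 15").
- Covariate and covariance: the final model takes each participant's "baseline (pre-treatment) accuracy at week 0 as a covariate, using heterogeneous first-order autoregressive variance and correlation structure".
- Other fixed effects: "Fixed effects include Groups as the combination of Treatment Distribution, Biofeedback and Modality, time points and their interaction". Time is categorical, and participants are random effects.
- Estimation: "Restricted maximum likelihood is used to estimate covariance parameters".
- Contrasts: these are built to "test the difference between treatment groups in terms of the improvement between baseline and week 5, 10, 15, respectively".
- Primary comparison: "The primary analysis is a comparison of change in percent correct from pre-treatment to the 10-week period".

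No sentence removes week 0 from the response once it becomes a covariate, and no baseline-by-time term is stated. The row unit is not stated either. Protocol 4.1 describes three individual phrase probe lists at Baseline 2 and at each progress assessment, so one row per child per visit and one row per probe list are both possible.

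**The concern.** A baseline value can be a response in a longitudinal model or a covariate in an adjusted model. Here the same number appears on both sides of the equation for the week-0 rows. Two consequences follow from taking the text at its word.

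1. The week-0 rows can be predicted perfectly. Heterogeneous AR(1) gives week 0 its own variance, so the likelihood can be driven up without limit.
2. The covariate enters with one slope at every visit, so it subtracts out of any change from week 0.

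This is the model for the primary week-10 comparison of both factors, in a trial planned for about 40 children (Protocol 7.1). A reader cannot tell whether the primary estimate is an unadjusted change-score difference or a baseline-adjusted difference. The two are not the same number on the same data.

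**Working it through.** **Inputs.** From the documents: 40 children; 4 groups in the 2 x 2 design (Protocol Table 1), or up to 8 cells when Modality is added as in the SAP; four time points; heterogeneous AR(1); REML. The SAP states no power, SD, correlation or effect size, so there is no figure to reproduce. All SDs and correlations below are assumptions.

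**1. The likelihood, with one row per child per visit.** The week-0 row for child i in group g is Y_i0 = mu_g0 + beta x Y_i0 + e_i0. Setting beta = 1 and mu_g0 = 0 makes every e_i0 zero. As the week-0 SD s0 shrinks, the n week-0 rows contribute -n x ln(s0). The REML term gives back (G + 1) x ln(s0) for the G week-0 means and the slope. The net is -(n - G - 1) x ln(s0), so each ten-fold fall in s0 gains (n - G - 1) x ln 10:

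- G = 4: 35 x 2.3026 = 80.6
- G = 8: 31 x 2.3026 = 71.4

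A numerical check used 40 simulated children with SDs 15/20/25/25, correlation 0.45, 4 groups and no random intercept:

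| Week-0 SD | 10 | 1 | 0.1 | 0.01 | 0.001 |
|---|---|---|---|---|---|
| REML log-likelihood | -615.3 | -534.7 | -454.1 | -373.5 | -292.9 |

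Each step gains 80.6, and the slope tends to 1.000. On a separate simulated dataset, 20 optimiser runs (five starts, with and without a random intercept, 4 and 8 groups) all drifted to this boundary. They stopped at log-likelihoods from about -245 to +529. None found an interior maximum.

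**2. The random intercept.** If the participant SD tau is held at a positive value, the week-0 marginal variance cannot fall below tau squared and the likelihood levels off. In one simulated dataset with tau = 5 it was -628.4, -601.1, -600.5, -600.5 and -600.5 at the same five week-0 SDs. Divergence returns when tau shrinks with s0, again at 80.6 per ten-fold fall. Because tau is estimated, that path is open and the fit remains unbounded.

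**3. Probe-list rows.** With two rows per child per visit and the child's mean as covariate, slope 1 no longer fits each week-0 row exactly. Among the week-0 SDs tried (16, 10, 8, 5, 2, 1, 0.1), the likelihood was highest at 8, so a maximum exists.

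**4. Cancellation, with complete data.** For any covariance matrix, the estimated mean vector of group g is ybar_g - beta_hat x ybar_g0 x (1,1,1,1)'. A change contrast c has weights that sum to zero, so c'mu_hat_g = c'ybar_g whatever beta_hat is. In the dataset tabulated above, the week-10 contrast was 4.372, the raw change difference, at every week-0 SD. It was also the raw difference (-3.898) in the probe-row simulation. With missing visits the cancellation is no longer exact, but the likelihood still has no maximum under one row per visit.

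**5. The two well-defined alternatives, on the tabulated dataset.**

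- Weeks 5, 10 and 15 only, adjusted for week 0: finite maximum, contrast 5.097, SE 7.720. Using change as the response gives the same contrast and SE; only the slope moves, from 0.693 to 0.693 - 1 = -0.307.
- Week 0 as a response without the covariate: finite maximum, contrast 4.372, SE 8.50.

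These values show only that the estimates differ. They are not predictions for this trial.

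**6. Precision.** SE ratio, change score over week-10 ANCOVA = sqrt(s0² + s10² - 2 r s0 s10) / (s10 x sqrt(1 - r²)), where s0 and s10 are now the outcome SDs at weeks 0 and 10. If ANCOVA has 80% power, change-score power is Phi(2.80/ratio - 1.96).

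| Assumed SDs (week 0, week 10) | r | Ratio | Power |
|---|---|---|---|
| 15, 25 | 0.3 | 25/23.85 = 1.05 | 76% |
| 15, 25 | 0.6 | 20/20 = 1.00 | 80% |
| equal | 0.3 | sqrt(2/1.3) = 1.24 | 62% |
| equal | 0.6 | sqrt(2/1.6) = 1.12 | 71% |

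**The case against.** The strongest reply is that the list of weeks may only describe the assessment schedule. The sentence about the final model follows text on model selection, and modelling weeks 5, 10 and 15 adjusted for week 0 is routine. That model is sound and delivers the stated comparison, because the baseline-adjusted group difference at week 10 equals the adjusted difference in change. This stands as a plausible intention. It does not cure the text, which names week 0 as a modelled response.

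A second reply is that the unbounded likelihood depends on one row per child per visit, which the SAP never states, and on the participant variance also going to zero. Both conditions are real and belong to the claim.

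A third is that a raw change-score difference is exactly what the SAP calls its primary analysis. That is fair: the cancellation makes the covariate inert but does not make the estimate wrong. The covariate can still alter the estimated covariance, and through it the reported SE and degrees of freedom.

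A reader might infer that the degenerate model was actually fitted, or that the primary result is biased or has inflated type I error. The documents support neither. They do not show which model was run. The change-score estimate is unbiased, and simulated null rejection was 4.5 to 5.3% for both the change-score and ANCOVA tests.

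**Conclusion.** The point holds as a defect in how the primary model is specified. With one row per child per visit, the model as written has no REML maximum, on the path where the week-0 residual variance and any random-intercept variance go to zero together. Software may still print output, but the numbers would depend on starting values and stopping rules. With probe-list rows the fit is defined. Under both row structures, complete data and a common slope leave the stated baseline adjustment with no effect on the primary point estimate.

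The two algebraic results need no assumed SDs. The practical size does. For correlations of 0.3 to 0.6, the change-score SE is 1.00 to 1.05 times the ANCOVA SE with SDs 15 then 25, and 1.12 to 1.24 times with equal SDs. The loss may therefore be nil. In simulated trials with ANCOVA power of about 76 to 77%, the two analyses fell on different sides of p = .05 in 3.5 to 8.6% of trials under the first set of SDs and 14 to 23% under the second. A primary analysis should not leave that choice open.

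**What to change.** Use week 0 once.

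- **Preferred:** remove week 0 from the dependent-variable time points, model weeks 5, 10 and 15 with week-0 accuracy as a covariate, and define the primary contrast as the baseline-adjusted group difference at week 10. A baseline-by-time term is optional.
- **Alternative:** keep week 0 as a response, drop the covariate, and say that the primary estimate is the unadjusted difference in change.

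In either case, state whether rows are per child or per probe list and, if per probe list, how the baseline value is formed. The cost is one or two sentences in the SAP and no new data. A re-run is needed only if the literal model was fitted.
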